1.1 Background

1.1.1 Scleroderma (systemic sclerosis)

Systemic sclerosis (SSc) is an uncommon, multisystem autoimmune disease characterized by small vessel vasculopathy, immune system activation with autoantibody production and fibroblast dysfunction leading to increased deposition of extracellular matrix.

SSc is an orphan disease with an incidence of nearly 20 patients per million per year (1,2) and an estimated point prevalence of approximately 250 per million based on US studies (2). SSc is a female-predominant disease, affecting women three to four times more often than men. SSc may affect individuals of all ages, with the peak incidence occurring between 45 and 64 years of age (2).

The hallmark of SSc is cutaneous and visceral fibrosis, which is reflected in the commonly used term for the disease, scleroderma, which derives from the Greek ‘scleros’ meaning thick and ‘derma’ referring to skin. While the cutaneous manifestations are the most obvious, it is the vascular and internal organ manifestations that contribute most importantly to disease morbidity and mortality.

SSc is described as two primary clinical subsets based on the extent of skin thickening: diffuse and limited cutaneous disease. Patients with limited skin disease have no skin thickening or skin thickening limited to the distal extremities (below the elbows and knees, but may have thickness of the face). Diffuse cutaneous patients experience similar distal changes, but also develop skin thickening proximal to the elbows and knees (upper arms, thighs, trunk) during the disease course. This clinical classification is useful as the natural history of the disease is different between the clinical subsets. Diffuse SSc patients develop progressive skin thickening and internal organ involvement early in their disease (first 2-3 years). The natural history of diffuse SSc skin thickening is that it may slowly improve over time even if untreated. Patients with limited SSc tend to develop no or minimal progressive skin changes over time, but may develop new internal organ involvement (particularly vascular complications) years into their disease.

Of the connective tissue diseases, SSc has the highest case specific mortality (3). Published estimates of mortality consistently report lower survival in the diffuse cutaneous SSc subtype compared to the limited SSc subtype (4-7).

SSc has a strong association with morbidity, disability and cost. Just over twenty years ago (1997) Wilson estimated the combined direct and indirect cost of care for SSc patients to be 1.46 billion dollars annually in the US (8). In 2015 a study performed in France assessed the average annual cost of SSc per patient to be 22,459 Euros (25,193 USD) (9). Of this, 10,526 Euros (11,807 USD) was an indirect cost due to an average SSc patient’s absence from the labor market.

1.1.2 Fatigue in SSc

Fatigue is defined as an abnormal bodily tiredness that is disproportionate to activity and unrelieved by rest. The term can be used to describe difficulty or inability to initiate activity (subjective sense of weakness); reduced capacity to maintain activity (easy fatigability); or difficulty with concentration, memory, and emotional stability (mental fatigue) (10). Subacute and chronic fatigue are common in many rheumatologic conditions, like fibromyalgia, polymyalgia rheumatica,

systemic lupus erythematosus, rheumatoid arthritis, and Sjögren's syndrome (11).

SSc patients frequently have fatigue as a characteristic feature of their disease and fatigue negatively impacts quality of life (12-15). The prevalence of fatigue among SSc patients is 75%, with 61% ranking fatigue among their top three most distressing complaints. Fatigue is also associated with poor sleep quality, greater pain and depressive symptoms (16).

SSc patients, have a prevalence of fatigue that is significantly higher than the general population and similar to patients with rheumatoid arthritis, ankylosing spondylitis, systemic lupus erythematosus, and current cancer treatment (17). Fatigue has been identified as one of the main factors negatively affecting well-being (18) and it's been associated with fewer visits to doctors (19). Fatigue is one of the main predictors (20, 21) of work disability in SSc patients. Correlations have been shown between fatigue and high scores on two different depression scales that have been validated in SSc patients, the Patient Health Questionnaire (PHQ-9) and the Center for Epidemiologic Studies Depression Scale (CES-D) (22).

Fatigue's recalcitrance to treatment in SSc patients has been shown in multiple longitudinal studies of symptom change over time (23-25). In a two-year longitudinal study of scleroderma patients' change in patient reported outcomes (PROs), fatigue worsened more than the other PROs, which included pain, sleep, disability and global health (26).

Treatment options for chronic fatigue are limited and the prognosis is not favorable (27). When the underlying medical cause of fatigue cannot be treated, treatment options include Cognitive Behavioral Therapy (CBT) and exercise (28, 29). If SSc patients exhibit depressive symptoms, treatment can involve an empiric trial of antidepressants (30). A systematic review of chronic fatigue's prognosis found that less than 10% of participants returned to pre-morbid levels of functioning, 10-20% worsened, and most remained significantly impaired. Risk factors for fatigue's poor prognosis are often present in SSc patients, and include older age, more chronic illness, having a comorbid psychiatric disorder and holding a belief that the illness is due to physical causes (21).

1.2 The Apollo Device

The Apollo System offers a convenient novel non-invasive, non-habit-forming wearable solution to improve performance and recovery under stress in children and adults by delivering gentle wave-like vibrations to the body that improve autonomic nervous system tone in near real time (Siegle & Rabin et al., under review). Apollo is about the size of an Apple Watch and can be worn on the ankle, wrist, or arm with two adjustable fabric straps. Apollo vibrations activate touch receptors in the skin and are perceived as safety signals by the brain resulting in decreased stress, improved recovery, focus, and energy.

In addition to the wearable, Apollo is a software system that curates music for the body, rather than for the ears. The scientific principles guiding the use of Apollo and our mechanistic understanding of its effects on the body are consistent with our understanding of how music and therapeutic touch effect the body to convey feelings of energy, focus, or relaxation by sending safety signals to the emotional cortex (limbic system) in the brain. Similar to music and touch used to facilitate a healing response in the body, there are no known side effects to this type of therapy.

Prior studies of Apollo have demonstrated significant improvements in fatigue and energy in healthy subjects in the real world as well as in subjects with chronic illnesses in clinical trials of Apollo within just a few days of use. Early findings strongly suggest that by improving autonomic tone, Apollo is attenuating biomarkers of persistent unwanted sympathetic activity, such as low heart rate variability (HRV), that over time, correlate with worse prognoses in many chronic illnesses. Low HRV is also a predictive factor in fatigue and poor energy recovery. Not only has Apollo been demonstrated to improve HRV and decrease heart rate, respirations, blood pressure, and other

markers of stress when threat is misappropriated, but it also appears to be inducing Meyer wave patterns in the vasculature (study data under analysis), which are known to correspond with nitric oxide release. As such, there is significant reason to believe that Apollo will improve symptoms of fatigue, inflammation, and vascular dysfunction in subjects with SSc.

The gentle vibrations delivered by the Apollo System are extremely low intensity in that they are typically just barely noticeable or perceptible by the user. From >2000 use cases in subjects ages 4-95yo, there have been no reported adverse events. Additionally, the range of frequencies and intensities of the Apollo System have been safely used in numerous commercial products without adverse events reported. Consistent with learning effects observed in meditation and mindfulness practices on the autonomic nervous system, Apollo case study participants report that continued use of Apollo results in quicker onset and longer duration of benefit. As such, there is significant potential benefit to be gained by the subjects and non-significant risk in the use of this technology in this study, as was also deemed to be the case in all of the prior approved IRBs for studies of Apollo. The devices tested in this study are commercially available Apollo wearables, built to FDA regulatory requirements and HIPAA compliance.

The wearable device used in this and other clinical studies of Apollo has a button on it that can always be engaged by the subject at any time to turn the Apollo vibrations off or back on within less than a second. The wearable can also be controlled by the Apollo mobile app that will be installed on the subjects' mobile smartphones. As such, the locus of control is always in the hands of the subject, providing significantly more autonomy to patients in treatment, which is one healing aspect of the Apollo System.

1.3 Rationale of the study

Fatigue is the symptom ranked highest by SSc patients as affecting quality of life. Thus, any device, therapy or pharmacologic products that could improve fatigue may have great potential benefit with respect to the quality of life associated.

1.4 Benefit-risk assessment

There are currently no disease-specific pharmacotherapies or devices approved for systemic sclerosis in the US. Management of the disease and its symptoms are clearly an area of unmet need. Thus, the potential for benefit is high.

The risks associated with the Apollo system are primarily associated with discomfort in wearing the wrist or ankle band. The design of this pilot and feasibility study is such that the participant determines use, and they have the option to stop at any time. Therefore, the level of risk is minimal.

Risk of breach of confidentiality: All study data collected via the Apollo HIPAA-compliant mobile app will be de-identified and registered to a specific study email account that is not linked to any identifiable information from the user. All paper documents (including consent forms) will be kept in a locked filing cabinet inside of a locked office. In addition, an ongoing review of study procedures will be done to ensure that the privacy of subjects and confidentiality of data is not violated. All data will be deidentified with a password protected master list as the only linkage between names and subject identification numbers. Consent forms, as well as any forms with identifiable information listed will be kept in a locked filing cabinet, separately from each subjects deidentified experimental and interview data. All electronic data collected will be accessible only with a password that is provided to clinical study staff and those individuals responsible for collection, maintaining data integrity and analysis. After the retention period is over, all study records will be de-identified and the linkage codes master lists will be destroyed. Study records will be kept secure under double lock in an office space devoted to long-term

retention of data for the purposes of maintaining scientific integrity.

The Apollo system has been tested and independently validated by individual members of a number of different institutions in the military and many Veterans, several academics at Universities, >10 elite athletics clubs, in pediatric clinics, nursing homes, as well as in two University of Pittsburgh clinical trials with 6 more trials currently underway. The Company has over 2000 beta testers and has conducted over 500 long-term case studies with consistent results. The technology proposed here has also been tested in children (as young as age 4), geriatric users, and other extremely vulnerable populations (such as those with treatment-resistant PTSD) without any reported adverse reactions.

Participants will be informed about any and all potential risks. There are no known long-term risks to the subjects from any of the study procedures, which have been used safely on thousands of men, women, and children. All study personnel examine screening materials before asking the participant to engage in any of the study activities in order to minimize the risks associated with the study procedures. If any additional physiological or mental health conditions are revealed during the screening or enrollment, they will be discussed individually with the clinical team ([name] et al.) prior to officially enrolling the subject in the study. If results are best discussed with the participant's physician, the participant will be offered the opportunity to complete a release of information form allowing [name] to contact the participant's physician directly.

2. STUDY OBJECTIVES

The primary objective of this study is to provide preliminary data on the efficacy and tolerability of the Apollo device in the management of fatigue in SSc.

The primary efficacy outcome is the change from baseline to four weeks of intervention using the Apollo system in the PROMIS-Fatigue scale. This instrument that has been previously validated in multiple diseases.

2.1 Secondary objectives

The secondary objectives of this study are to provide preliminary data on indices of depression, health-related quality of life, Raynaud symptoms and tolerability/frequency of use with the Apollo device in SSc.

Specific secondary objective measures include:

- Depression, measured by the QUIDS-SR (16 item) score.
- Health-related quality of life (HRQOL) using PROMIS-29
- HAQ-DI
- Visual analog scales from scleroderma-health assessment questionnaire (SHAQ) assessing burden of digital ulcers, Raynaud's disease, gastrointestinal involvement, breathing, and overall disease
- Improvement of Raynaud's phenomenon (RP) (7, 8)
 - Raynaud's condition score
 - Raynaud visual analog scale
 - Patient and physician assessment of RP; pain, numbness, and tingling
 - RP frequency and duration of attacks based on one-day use of the Raynaud application used at baseline and two weeks.
-

3. INVESTIGATORS and PERSONNEL

Role: Investigator
Name and Contact Information: [name], MPH
University of Pittsburgh School of Medicine
[name]
[name]
[name]
[contact]
Email: [contact]

Role: Research coordinator
Name and Contact Information: [name], BA
University of Pittsburgh School of Medicine
[name]
[name]
[name]
[contact]
Email: [contact]

Role: Graduate student / research assistant
Name and Contact Information: [name]

Data Safety and Monitoring Plan

A data and safety monitoring plan will be implemented by the Principal Investigator to ensure that there are no changes in the risk/benefit ration during the course of the study and that confidentiality of research data is maintained. Each member of the study team will meet with the PI and review confidentiality issues and complete a confidentiality agreement, prior to having contact with research subjects. Investigators and study personnel will meet **every 2 months** to discuss the study (e.g. study goals and modifications of those goals; subject recruitment and retention; progress in data coding and analysis; documentation, identification of adverse events or research subject complaints; violations of confidentiality) and address any issues or concerns at that time. Minutes will be kept for these meetings and will be maintained in the study regulatory binder. Any instances of adverse events will be reported immediately to the University of Pittsburgh IRB. The IRB renewal for this study will include a summary report of the Data and Safety Monitoring Plan findings from prior renewal period.

4. STUDY DESIGN

4.1 Design overview

This clinical trial is a single-center, open-label, single-arm study of 30 individuals with SSc and fatigue.

The study will allow for subjects to continue standard of care medications for the management of SSc as background therapy.

The study design consists of a single, four-week intervention. The screening and baseline visits can be combined when the screening is not able to be performed over the phone in advance.

- **Screening phase:** up to 4 weeks prior to baseline visit
- **Observation period:** During this one week phase participants will track their daily Raynaud attack frequency and duration using a diary. This will occur in the seven days preceding the baseline intervention phase.
- **Open-label intervention phase:** This consists of a four-week period during which participants will use the Apollo wearable system as needed to manage symptoms including fatigue. During the intervention phase participants may use the wearable at their discretion and control. Participants will track their daily Raynaud attack frequency and duration using a diary during week 4 of Apollo use. Participants will complete questionnaires on day 1 of the open-label and intervention phase, and at their follow-up four weeks later.

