4.1.1 Screening phase (up to 4 weeks prior to baseline visit)

After providing written informed consent, participants will undergo a screening evaluation to determine their eligibility (see Section [7.1](#) for a detailed schedule of events). Participants will complete the PROMIS-Fatigue scale to determine if they have moderate to severe fatigue. If a T score of 45 is obtained, and all inclusion criteria are met, then the patient may proceed to the observation phase. Participants will be given the 7-day diary to be completed starting one week prior to their scheduled baseline visit. They will be reminded by telephone call or text (based on

their preference) to begin their diary collection.

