4.1.2 Intervention Phase

At the baseline visit, participants who have met all of the inclusion criteria. At this visit they will complete the following questionnaires:

- 1) PROMIS-fatigue
- 2) PROMIS-29
- 3) The QUIDS-SR
- 4) HAQ-DQ with SHAQ
- 5) Raynaud condition score, Raynaud visual analog scale and digital ulcer visual analog scale

They will then be provided the wearable Apollo system device. They will download the mobile application, and be taught how to install it and use it to control the wearable Apollo device by the research coordinator(s). Any questions will be answered at this time. Participants will be able to use the device from the time they leave the visit. Use of the device will be entirely at the subject's control.

In the week prior to their end-of-study visit, participants will complete a daily diary collection of Raynaud attack episodes and symptoms using the paper diary form. This will be provided prior to leaving the baseline visit.

Participants will be sent a reminder call or text the day before and day they are to begin their diary collection on one week prior to their scheduled end-of-study visit.

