7.1.2.2 Visit 1 – Baseline

The following assessments will be performed at the Baseline visit

- Reconfirmation of eligibility
- PROMIS-fatigue scale administered
- Patient reported outcomes (QUIDS-SR, patient global assessment, PROMIS-29, HAQ-D1/SHAQ, visual analog scales) and physician global assessment
- Vital signs (blood pressure and heart rate). The blood pressure is measured in a sitting

position after the participant has been at rest for at least 5 minutes. The same arm is always used for these measurements

- Digital ulcer assessment
- Assessment of Raynaud attacks – participant provided the one-day diary and RCS to complete the day following the screening
- Recording and assessment of AEs (see Section [7.5.1.3](#))
- Downloading of the mobile application and teaching of how to use the Apollo wearable device. The participants will be allowed to use it up to 30 minutes to familiarize themselves with the working of the device while at this visit.

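### A combined screening and baseline visit leaves no pre-device days for the Raynaud diary, and the protocol sets that diary at both seven days and one day

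*Combined protocol and SAP*

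**What the plan says.** **Visits.** Section 4.1 (Design overview): "The screening and baseline visits can be combined when the screening is not able to be performed over the phone in advance".

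**First diary.** Section 4.1 describes a one-week observation period for recording Raynaud attacks: "This will occur in the seven days preceding the baseline intervention phase". Section 4.1.1 issues the form once the participant has consented and qualified: "Participants will be given the 7-day diary to be completed starting one week prior to their scheduled baseline visit". Section 7.1.2.1 allows screening evaluations only after written consent.

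**Device start.** At the baseline visit (7.1.2.2): "The participants will be allowed to use it up to 30 minutes to familiarize themselves". Section 4.1.2 adds: "Participants will be able to use the device from the time they leave the visit".

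**Final diary.** Section 4.1: "Participants will track their daily Raynaud attack frequency and duration using a diary during week 4 of Apollo use". Section 4.1.2 asks, in the week before the last visit, for a "daily diary collection of Raynaud attack episodes and symptoms using the paper diary form".

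**Raynaud measures taken at the baseline visit itself.** Section 4.1.2 lists "Raynaud condition score, Raynaud visual analog scale and digital ulcer visual analog scale".

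**One-day wording.** Section 2.1 bases attack frequency and duration on one day's use of a Raynaud application, at baseline and at two weeks. Section 7.1.2.2 lists a one-day diary under the baseline visit, to be filled in on the day after screening. Section 7.6.1 first asks for a daily diary over a week. Its frequency line then asks for one day in the observation period and one day just before the final visit.

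**The concern.** The trial has no control arm, so the pre-device value is the only comparator for every change score. If the visit structure allows the device to be handed over before any diary day has been recorded, the change in the diary items is missing for that participant. The alternative is worse: a diary filled in after handover might be treated as baseline, and any effect already present would then be subtracted from itself. A lost pre-device diary cannot be recovered later.

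The conflict over diary length is a separate matter and does not depend on combined visits. Staff working from different sections would collect one day from some participants and seven from others, and both would enter one analysis.

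**Working it through.** **1. Day count.** Put screening and consent at day −g and baseline with device handover at day 0. The diary can be issued no earlier than screening, so

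pre-device diary days = min(7, g).

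The plan's own figure of seven days is reproduced whenever g is 7 or more, which fits inside the screening window of up to 28 days.

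| Gap g (days) | Pre-device diary days |
|---|---|
| 7 to 28 | 7 of 7 |
| 6 | 6 of 7 |
| 3 | 3 of 7 |
| 1 | 1 of 7 |
| 0 (combined visit) | 0 of 7 |

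**2. Does the one-day version in 7.1.2.2 rescue it?** Its diary day is −g + 1. For g = 0 this is day +1, after handover. For g = 1 it is day 0, the baseline visit day. It is before day 0 by date only when g is 2 or more. But 7.1.2.2 hands the diary out at the baseline visit, when that day has already passed. Read literally, 7.1.2.2 does not deliver a pre-device diary day at any gap.

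**3. Diary length and timing side by side.**

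| Section | First diary | Final diary |
|---|---|---|
| 2.1 | one day, baseline | one day, two weeks |
| 4.1 | seven days before intervention | daily in week 4 |
| 4.1.1 | seven days before baseline | – |
| 4.1.2 | – | daily in the week before the final visit, on paper |
| 7.1.2.2 | one day, the day after screening | – |
| 7.6.1, diary sentence | seven days | seven days |
| 7.6.1, frequency line | one day in the observation period | one day, the day before the final visit |

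Section 7.6.1 contradicts itself. Section 2.1 also names an application where 4.1.2 names a paper form.

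**4. What is missing after a combined visit.** Sections 4.1 and 7.6.1 put attack frequency and duration in the diary, and 7.6.1 adds the daily Raynaud condition score. These have no pre-device diary value. Attack symptoms appear only in the description of the end-of-study diary in 4.1.2; they are also missing if the first diary uses the same form, which is an assumption. The condition score and visual analog scale completed at the baseline visit remain.

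**5. Size.** The share s of combined visits is not given. With 30 participants, the number with a computable diary change is 30 × (1 − s). For a mean change, the 95% interval half-width in units of the SD of change is t(0.975, n − 1)/√n.

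| Assumed s | n | Half-width | Ratio to n = 30 |
|---|---|---|---|
| 0% | 30 | 0.373 | 1.00 |
| 10% | 27 | 0.396 | 1.06 |
| 20% | 24 | 0.422 | 1.13 |

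This is a guide only, since 8.2.2 plans Poisson regression for counts.

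**6. One day against seven.** Assume an equal correlation ρ between any two diary days. The between-patient SD of a one-day value relative to a seven-day mean is √(1/(ρ + (1 − ρ)/7)). For ρ = 0.3, 0.5, 0.7 and 0.9 this is 1.58, 1.32, 1.16 and 1.05. The documents give no ρ. The two lengths estimate a daily rate with different precision, so mixing them is not harmless.

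**The case against.** The combined visit is a fallback for when telephone screening is not possible, and it may seldom or never occur. That stands: the share is unknown and may be zero. It does not touch the length conflict, which applies to everyone.

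In the schedule (7.1), the baseline diary cell carries a superscript c whose footnote is not in the text available here. It may address timing. That stands too, so it cannot be said that the protocol is silent on combined visits, only that the visible text gives no rule. A footnote to one cell would still leave 2.1, 4.1, 7.1.2.2 and 7.6.1 saying different things.

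The outcomes concerned are secondary, in a pilot whose analysis section 8.1 describes as largely descriptive and hypothesis-generating. That limits the weight of the point.

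A reader might go further in four ways that the documents do not support:

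- *That the six-measure Raynaud composite cannot be computed.* Section 7.6.1 names a composite but gives no formula, weights or rule for missing components, and neither 7.3 nor 8.2.2 mentions one. What follows is only that certain items lack a pre-device value.
- *That the Raynaud baseline is lost altogether.* The condition score and visual analog scale from the visit survive.
- *That the primary endpoint is compromised.* The schedule lists PROMIS-Fatigue at screening and again at baseline. How the qualifying score relates to the baseline score is a separate question.
- *That a post-handover diary would cause a known bias.* Section 1.2 claims a rapid effect on autonomic tone, not on Raynaud attacks, so the documents give no size for an early effect.

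**Conclusion.** The point holds on the text, in two parts. First, a combined visit with same-day handover gives 0 of 7 pre-device diary days, and the one-day alternative falls after handover. Those participants have no pre-device attack number or duration and no daily diary condition score; attack symptoms are missing as well if one form is used throughout. Second, the first diary is both seven days and one day for every participant. The final diary is placed in week 4 or the last week, on the day before the final visit, or at two weeks.

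The day count needs no assumption beyond the order consent, diary, device that the protocol itself sets. The numerical loss does rest on assumption: 30, 27 or 24 of 30 participants with a computable diary change at combined-visit shares of 0%, 10% or 20%. The unseen footnote could soften the first part. The effect is confined to secondary, descriptive Raynaud outcomes. It should be corrected, but it does not threaten the PROMIS-Fatigue result.

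**What to change.** - Reconcile 2.1, 4.1, 4.1.1, 4.1.2, 7.1.2.2 and 7.6.1 to one diary length, one timing for each diary and one medium. The sponsor must confirm which length is intended, because the documents support both.
- Correct 7.1.2.2 so that the first diary is issued at screening and completed before first device use, whichever length is chosen. This means either dropping the combined visit or separating device handover from it.
- If combined visits with same-day handover stay, state that those participants are excluded from diary-change analyses, report their number, and state that a diary completed after handover is not used as baseline.
- Confirm what footnote c in the schedule says about diary timing.

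**Cost.** One further contact for each participant who would have had a combined visit, possibly a clinic visit because the schedule lists screening as an office contact. The exclusion route needs no extra contact but loses those participants' diary-change data. If seven days is confirmed, each participant completes 7 + 7 = 14 diary days; if one day, 1 + 1 = 2. The remaining changes are to wording only.
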